**NCT04817891**

## SPECIFIC AIMS

Fluctuating cognition is a characteristic core diagnostic feature of dementia with Lewy bodies (DLB) and is also a key clinical feature of Parkinson's disease with dementia (PDD) (1, 2). Cognitive fluctuations are a major source of disability in these Alzheimer-related Lewy body dementias (LBD) (4). The **central premise** of this R21 proposal is that cholinergic system changes in specific neural network regions underlie cognitive fluctuations in patients with LBD. Several independent lines of evidence implicate the cholinergic system in LBD. *First*, ex vivo post-mortem and *in vivo* acetylcholinesterase brain PET imaging studies have shown prominent cholinergic losses in LBD (5). In novel preliminary data using a vesicular acetylcholine transporter (VAChT) PET ligand, we extend these findings to show regionally distinct and prominent reductions in bilateral opercula and anterior-to-mid cingulate cortices, bilateral insula, and other areas that are part of the cingulo-opercular task control (COTC) network (14) in patients with DLB. **Therefore, the specific topography of cholinergic reductions in these DLB patients suggests preferential cholinergic involvement of the COTC network.** The COTC neural network is believed to play a role in maintenance of alertness (15, 16) but this remains uncertain in LDB. This **critical knowledge gap** forms the basis of **our first aim**. We postulate that cholinergic losses in key COTC neural network hubs may underlie cognitive fluctuations in LBD. *Second*, there is clinical evidence that cognitive fluctuations in LBD are amenable to treatment with cholinesterase inhibitor drugs (19). However, the efficacy of current generation cholinesterase inhibitor drugs is typically limited due to poor brain penetrance (22). Novel approaches are needed to address this clinical unmet need. We propose to use transcranial direct current stimulation (tDCS) to "excite" critical cholinergic denervation components of the COTC as an adjunct to cholinergic pharmacotherapy in a target engagement study. tDCS is an emerging non-invasive neurostimulation technology that may improve a range of neurological symptoms, including cognition. There is also evidence that tDCS may modulate cholinergic activity modulation (25). Several small studies have employed tDCS in patients with LBD and revealed encouraging improvements in attention (26), though none have examined cognitive fluctuations to date. In the **exploratory aim** we will evaluate whether target engagement by tDCS excitation of cholinergic denervated COTC hubs may affect cognitive fluctuations in LBD subjects.

**Specific Aim 1:** To perform detailed clinical evaluation, including measures of cognitive fluctuations, F-fluoroethoxybenzovesamicol (F-FEOBV) VAChT PET, and brain MR imaging, in patients with LBD (n=18 enrolled; Net target completion rate = 12) in order to evaluate COTC integrity and the functional ramifications of dysfunction.

**Hypothesis 1:** Severity of cognitive fluctuations associates with greater cholinergic deficits in COTC network regions in patients with LBD. We will evaluate subjective measures of fluctuations as well as objective measures of working memory and cognitive control that depend on the COTC and presumably underlie such fluctuations.

**Exploratory aim 2:** To perform a target engagement study of 10 consecutive daily sessions of individualized tDCS to excite the bilateral opercular and anterior cingulum hubs of the COTC alertness network in patients with LBD. We will use a unique approach of creating MRI-based and VAChT PET-informed participant-specific computer models of electrical current flow through the brain in order to optimize stimulation effects and more precisely target the dysfunctional networks. tDCS dosing is traditionally defined by the amount of electrical current delivered at the scalp (e.g., 2mA); however, this neglects the individual differences in brain morphology that are known to affect the delivered dose (i.e., how much electricity reaches the brain). Thus, we will prospectively apply the MRI-based models to ensure a consistent dose is delivered to the targeted brain regions, selected from the VAChT PET scans, across participants. This approach substantially advances the field of tDCS and maximizes the probability of response at the individual level.

Exploratory hypothesis: tDCS excitation of key vulnerable cholinergic hubs of the cingulo-opercular alertness network will improve cognitive fluctuations in patients with LBD.

Positive findings of this study will advance our **scientific understanding** of the role of key hubs of the COTC network in the etiology of cognitive fluctuations in LBD. Moreover, positive findings of the exploratory target engagement study may provide the impetus for clinical trials of cholinergic augmentation with adjunct tDCS therapy for cognitive fluctuations symptom relief to enhance everyday functioning in LBD patients.

## RESEARCH STRATEGY

**Significance:** Fluctuations in attention and alertness are a major source of disability for subjects with LBD. Current clinical treatment approaches are mainly based on pharmacotherapy but have limited clinical effectiveness. The COTC neural network is believed to play a key role in maintenance of alertness. Based on preliminary data of the topography of cholinergic denervation changes in persons with LBD we hypothesize that cholinergic denervation of this alertness network plays an important role in the pathophysiology of cognitive fluctuations in LBD. Our exploratory target engagement study proposes to examine the effects of non-invasive tDCS excitation of cholinergic denervation hubs in this network. Positive findings of this study could spur future clinical trials of targeted non-invasive neurostimulation using tDCS as adjunct to cholinergic pharmacotherapy as a novel way to manage fluctuations in alertness in people with LBD.

**Innovation:** There is a **high level of innovation** in this proposal as we take advantage of recent neuro-imaging advances of cholinergic VAChT PET imaging and MR-based large-scale neural network identification in LBD. These include (i) the evaluation of novel regionally distinct cholinergic system changes associated with key hubs of the COTC neural network, implicated in maintenance of tonic alertness; (ii) the proposed research will develop a non-invasive neural network stimulation approach to boost and complement the limited brain penetrance of currently used cholinesterase inhibitor drugs in DLB; (iii) We will take the unique approach of creating VAChT PET-informed participant-specific computer models of electrical current flow through the brain in order to optimize tDCS effects and more precisely target the dysfunctional networks. This approach substantially advances the field of tDCS and maximizes the probability of response at the individual level.

### Scientific premise

Cognitive fluctuations in LDB: Fluctuations in cognition and alertness are key manifestations of DLB (19). Fluctuating cognition is not only a core diagnostic feature but also the most characteristic feature of DLB (1, 2, 19). Fluctuating cognition is also a key clinical feature of PDD (27). Cognitive fluctuations consisting of pronounced variations in attention and alertness are a major source of disability of patients and caregivers alike (4). The exact underlying pathophysiological processes underlying cognitive fluctuations remain unclear. However, neuroimaging and neurophysiological techniques have recently provided insight into potential drivers of the phenomenon (4). Several mechanistic theories have been posited to explain the etiology of cognitive fluctuations. Most authorities hold that cognitive fluctuations are attributable to a separate pathophysiological process to that driving progressive cognitive decline, as fluctuations by nature are transient and reversible. Putative pathophysiological models include fluctuations in cognition as an attentional disorder, as a consequence of loss of cholinergic drive, as a manifestation of failure in neuronal efficiency and synchrony, or as a disorder of sleep/arousal (4). Evidence for a hypocholinergic etiology is further provided by a highly selective animal lesion model, which demonstrated a correlate of fluctuating cognition with variable response latencies on an attention task in rats subjected to cholinergic denervation of the pedunculopontine tegmental nucleus, which is functionally linked to the cholinergic forebrain (28). The argument is further buttressed by data from both mechanistic (29) and clinical studies (30, 31) identifying improvements - albeit modest - in fluctuating cognition in patients treated with cholinesterase inhibitors.

Large-scale neural networks and cognitive fluctuations: Graph theory analysis of functional connectivity resting state MRI has identified two distinct top-down task-control networks involved in attention (14, 32). The dorsolateral prefrontal cortex and intraparietal sulcus are hubs within the frontoparietal task control (FPTC) network. The FPTC network is important for start-cue and error-related activity and may initiate and adapt control on a *more rapid* and trial-by-trial basis. The COTC network encompasses medial superior frontal cortex, dorsal anterior cingulate, frontal operculum, anterior insula and thalamic regions (14). Effectively, the COTC graph may include parts of both the large-scale distributed network of the cingulo-opercular and salience networks (14, 32, 33). The COTC network has been implicated in important cognitive functions, including sustaining alertness, task set maintenance and salience detection of stimuli (14, 16, 34). Hence, the COTC network controls goal-directed behavior more on a set maintenance mode *using a longer duration time scale*, such as needed for maintenance of alertness (15). Clinically, this may be reflected in a lack of maintenance of a functional operative state and difficulties staying on task in DLB persons in their daily life functions resulting in cognitive fluctuations. Morphometric studies have shown atrophy in the right anterior cingulate cortex and bilateral insular regions in

patients with prodromal DLB, 93% of who exhibited fluctuating cognition (35, 36). A prior resting state fMRI network study found evidence that cognitive fluctuations in patients with DLB correlated with widespread brain regions, including opercular/insular and anterior cingulum regions (37). These regions are implicated in the integrity of attentional circuits, and therefore provide supportive evidence for attentional impairments in cognitive fluctuations (38).

**tDCS in LBD is in a nascent stage.** Briefly, tDCS modulates neuronal excitability (i.e., the probability of neuronal firing) by passing a low intensity electric current between electrodes that are typically placed on the scalp according to the international 10-20 (or 10-10) system. This same measurement system is used with EEG and provides a standardized, accepted, and clinically friendly placement method. tDCS electrodes are either characterized as an anode that “introduces” the electrical current or a cathode that “collects” the current. Evidence suggests that neuronal soma under the anode(s) consistently become depolarized (“excited”) (39, 40). Single session effects can last 60-90 minutes (41) and can be extended by consecutive daily sessions (see (42). Only a single tDCS study in those with DLB focused on arousal/attention. That study reported improved attention following a single session of tDCS (2.8mA) when the anode was placed over the left dorsolateral prefrontal cortex and the cathode over the right deltoid (26). Evidence from related alpha-synucleinopathies ( $\alpha$ -Syns), particularly Parkinson disease (PD), have been favorable as reflected by enhanced working memory after 2mA over the prefrontal cortex (43, 44) as well as by enhanced phonemic fluency and functional connectivity of brain regions mediating such cognitive abilities (45).

[figure not shown]
**Impact:** This project builds on novel FEOBV findings, ongoing work with tDCS, and a unique patient cohort at the University of Michigan MADRC and the Ann Arbor VAMC. Promising findings in the study may augur novel neurostimulation targets to enhance cholinergic network maintenance of arousal and alertness in LBD.

**Preliminary data: Topography of cholinergic vulnerability in patients with DLB using VAChT PET:** Five DLB subjects and 21 normal control elderly underwent clinical assessment and  $^{18}\text{F}$ -FEOBV PET imaging. Compared to the control group, reduced VAChT binding in DLB patients demonstrated non-diffuse but regionally distinct and prominent reductions in bilateral opercula and anterior-to-mid cingulate cortices, bilateral insula, right more than left lateral geniculate nuclei, pulvinar, right proximal optic radiation, bilateral anterior and superior thalamus, and posterior hippocampal fimbria and fornices (Fig. 1). With respect to the extent of these topographic changes major hubs of the COTC network predominate the observed cholinergic denervation changes in the DLB patients.

**Figure 1:** Reduced cholinergic binding in key areas associated with alertness (cingulo-opercular) networks, saliency (insula), visual attention (visual thalamus), spatial navigation (fimbria/fornix). Spatial extent of changes is most prominent for the COTC network hubs.

**Figure 2:** Data-driven cholinergic sub-networks in PD. The sub-network shown in green color has striking topographic overlap with the COTC.

[figure not shown]
**Figure 3:** Pyramid of cognitive functions (modified after Scott, 2011).

[figure not shown]
Data-driven cholinergic sub-networks defined by VAChT PET in PD. We performed a principal component analysis of whole brain VOIs from FEOBV PET scans in 86 patients with PD. Different factors are shown in different colors (Fig. 2). The green colored factor (third row) has striking topographic overlap with the COTC alertness network. Importantly, analysis of cognitive test performance showed significant cognitive correlates of the cholinergic binding in the COTC hubs across all cognitive domains (attention, language, visuospatial, memory and execution). Notably, the VAChT binding topography of significant voxel based correlations with the different cognitive domains showed overlapping areas that included key hubs of the COTC alertness network including the anterior cingulum and bilateral opercular regions. We hypothesize that the shared topography of cholinergic correlates of various cognitive domains correlates with findings of functional neuroimaging studies showing a core co-activation pattern as a result of cognitive task engagement *independent* of the specific task (34, 46). The term '*task-positive*' has been reserved for this type of co-activation of different brain regions during cognitive tasks (47). Hence, the general task activation pattern suggests an involvement of foundational capacities such attentional control *common* to cognitive performance in general (15), see also a simplified model of *shared 'sub-serving'* cognitive functions in Figure 3 (48).

Traditional tDCS dosing methods apply a pre-specified amount of electrical current to each participant via the scalp-based electrodes with the assumption that this yields comparable current delivery to the brain. However, this fails to account for individual morphological differences in "normal" brains as well as additional disease related changes, as would be expected in our LBD cohort. Our preliminary data are from 12 cognitively intact older adults who underwent high definition (HD) tDCS over the right parietal cortex (2mA for 20 minutes). In two separate sessions (randomized to active or sham), each participant completed an fMRI task (spatial navigation) and subsequent memory test after HD-tDCS. We then created individualized MRI-based finite element models of electrical current flow for each participant.

## Overall strategy

### Overview

The overarching goal of this proposal is to perform brain  $^{18}\text{F}$ -FEOBV VACHT PET and MRI and detailed clinical and cognitive characterization in at least 12 (n=18 enrolled; Net target completion rate = 12) patients with LBD who are on stable doses of cholinesterase inhibitors, *i.e.*, at least 4 weeks. In exploratory Aim 2, we will use MRI-guided finite element models that are informed by FEOBV PET imaging to create participant-specific computer models of electrical current flow through the brain in order to optimize stimulation effects and more precisely target COTC hubs via tDCS in a target engagement study. Assessment of cognitive fluctuations will be measured by the Dementia Cognitive Fluctuation Scale (49). Details on the baseline (pre-) and post tDCS testing protocol are listed in the General Methods.

Design & subjects and consideration of **relevant biological variables**, such as gender and age: Cross-sectional neuroimaging-clinical correlation study with exploratory non-invasive neurostimulation target engagement study. Although LBD affects men more than women, we will place special emphasis on equal recruitment of women. We have no *a priori* rationale to expect the findings to differ as a result of sex but will directly evaluate sex differences. Effects of age will also be taken into account.

Timeline and milestones: Gross recruitment for the project will be 18 persons with probable DLB while anticipating 12-18% attrition (net recruitment target n=12). We will recruit and test 8-9 persons per year (approximately one every 2 months). Subject recruitment and testing will be completed within the first 10 months

of year 2 to allow statistical analysis and write-up of the study findings. *Milestones* of success are net completion of 6 persons for year 1 by 12 months and a total of 12 by 10 months in year 2.

**Statistical analysis:** The primary objective of this proposal is to establish VAChT PET COTC neural network correlates of cognitive fluctuations. We will employ generalized linear mixed models (GLMM) to accommodate correlation via fixed and random predictor effects. GLMM has the advantage that it also allows for modeling of non-normal distributions and nonlinear models. The main predictors will be bilaterally averaged opercular, insular and anterior cingulum VAChT PET binding and the summed score of the 17-item Dementia Cognitive Fluctuation Scale (49). As LBD affect men more than women, gender will be included as a key biological variable in all analyses. Other co-variates will include measures of (motor) disease severity such as modified Hoehn and Yahr stage or MDS-UPDRS part III score, global cognition (MoCA), age, and levodopa equivalent dose and use of cholinergic drugs. Analysis of exploratory Aim 2 will use GLMM to evaluate the overall tDCS effects and regression analysis of the relationship between bilaterally averaged opercular, insular and anterior cingulum VAChT PET and tDCS changes in the Dementia Cognitive Fluctuations Scale. To avoid Type II error inflation correction for multiple testing will be performed. Statistical analysis will be performed by the Department of Radiology statistician [name].

**Expected results:** For aim 1, we predict that severity of cognitive fluctuations as measured by the Dementia Cognitive Fluctuation Scale (49) associate with greater cholinergic deficits in COTC network regions in patients with LBD. For our exploratory aim 2, we predict that tDCS targeting key hubs of the COTC neural network using VAChT PET-derived stimulation volumes will improve subjective and objective cognitive fluctuations in the LBD patients and as a function of the degree of cholinergic losses in the targeted regions.

**Sample size considerations:** Our main hypothesis will be tested using GLMM analysis. We have preliminary data obtained in persons with PD showing a correlation coefficient of  $R=0.59$  ( $P<0.001$ ) between COTC VAChT binding and attention/working memory functions yielding a power of  $>.95$  to find a significant correlation ( $P<0.05$ ). Exploratory aim 2 is a target engagement study to provide go/no go feasibility for future clinical trials.

**Pitfalls and alternative strategies: Effects of neural networks other than the COTC:** It is possible that large-scale neural networks other than the COTC may be more robust drivers of an association between cholinergic system changes and cognitive fluctuations than the COTC hubs per se. For this purpose, we will compute VAChT binding changes in hubs of networks, such as the dorsal attention, ventral attention or central executive networks for alternative analyses. The MRI based computational model (CM) for each participant allow us to determine the extent to which any such network effects were affected by tDCS, thereby parsing direct effects of stimulation (i.e., the electrical field – EF) delivered to the associated brain regions) from those arising from between-network connectivity changes. Given the nature of the R21 mechanism, our goal is to evaluate the feasibility of the proposed methods and detect any evidence of change in the outcome measures so we will not include a sham control group at this preliminary stage. Positive findings in this study will allow a subsequent R01 application to include an appropriate control group as in Co-PI [name]'s ongoing studies.

**Target engagement study:** We will perform an exploratory open-label tDCS target engagement study to provide causative evidence of cingulo-opercular alertness network involvement in the pathophysiology of cognitive fluctuations. Positive results will provide guidance for future clinical dose-finding trials. We propose 10 tDCS sessions based on Co-PI [name]'s experience with ongoing clinical trials and evidence of cumulative and persistent improvements following multiple sessions (typically  $\sim 5+$ ) in other populations (see (42). As an initial step, this design balances feasibility (i.e., participant burden) by providing a sufficient and known (via the EF maps) dosage for each participant.

**Effect of acetylcholinesterase inhibitor drugs on FEOBV binding:** We have selected the  $^{18}\text{F}$ -FEOBV PET radioligand because of its high affinity and selectivity binding to the VAChT based on stereospecificity of biological effects, pharmacologic blocking studies and *in vivo* brain autoradiography and metabolites studies (50). FEOBV PET studies appear to be not significantly affected by cholinesterase inhibitor drugs based on preliminary rodent data ([name], University of Michigan).

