## General methods

**Clinical characterization:** All subjects will undergo a general clinical assessment. Severity of motor parkinsonism will be assessed using the Movement Disorder Society-revised Unified Parkinson's Disease Rating Scale (MDS-

UPDRS) (51). Neuropsychological testing measures are presented in Table 1. Neurobehavioral and sleep assessment will consist of Epworth Sleepiness Scale for daytime somnolence (52); The Mayo Sleep Questionnaire for sleep quality and disturbances (53); The Spielberger State Trait Anxiety scale for trait anxiety levels (54). The Brief Psychiatric Rating Scale will be used for the assessment of hallucinations (55). We will use the Geriatric Depression Scale for the assessment of depression (56). The Apathy Evaluation Scale (AES) clinician version will be used to assess apathy severity (57). Patient on dopaminergic medications will be testing in the medication 'on' state. The test battery will be repeated after the target engagement tDCS study.

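### The Aim 1 power claim of above .95 does not hold at 12 to 18 patients, and the test it refers to is not pinned down

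*Combined protocol and SAP*

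**What the plan says.** Under Overall strategy, the Sample size considerations paragraph says the main hypothesis will be tested by GLMM. It cites preliminary data in Parkinson's disease, R=0.59 with P<0.001, for the correlation "between COTC VAChT binding and attention/working memory functions yielding a power of" above .95 at P<0.05. It states no sample size for that power and no sidedness. The Overview and the Timeline give 18 enrolled and a net target of 12, with 12-18% attrition expected.

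The Statistical analysis paragraph describes the model:

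- Model family: "We will employ generalized linear mixed models (GLMM) to accommodate correlation via fixed and random predictor effects". No random factor or grouping unit is named.
- Predictors: "The main predictors will be bilaterally averaged opercular, insular and anterior cingulum VAChT PET binding". It does not say whether the three hubs enter jointly, separately or as a composite. The fluctuation scale total appears in that same list of predictors.
- Covariates: gender in all analyses, and for motor severity an open choice, "measures of (motor) disease severity such as modified Hoehn and Yahr stage or MDS-UPDRS part III score". Four more are then listed without any coding or order of entry: "global cognition (MoCA), age, and levodopa equivalent dose and use of cholinergic drugs".
- Multiplicity: "To avoid Type II error inflation correction for multiple testing will be performed". The Scientific rigor paragraph adds family-wise and false discovery rate corrections where appropriate. Neither place names the family of tests.

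The Outcome measures section makes the Dementia Cognitive Fluctuations Scale (DCFS) the primary outcome. The Human Subjects section requires every patient to be on a stable cholinesterase inhibitor.

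**The concern.** Only Aim 2 is labelled exploratory. Aim 1 is the primary objective and carries a hypothesis and a power figure, so a reader will take a non-significant result as informative. With power above .95, a null result would count strongly against the hypothesis. With power near one half or lower, it says little.

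The stated power is for one unadjusted correlation. The analysis plan describes something bigger, with three hubs and up to six covariates, and does not say which result decides Aim 1. No single power figure can therefore be attached to the planned test until that test is named.

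**Working it through.** **Inputs from the plan.** r=0.59; alpha 0.05 (two-sided assumed, one-sided also shown); n=12 (net target) to 18 (enrolled). Attrition of 12-18% from 18 leaves 18 x 0.82 = 14.8 to 18 x 0.88 = 15.8, so n=15 is shown as well. Covariates: gender, motor severity, MoCA, age, levodopa equivalent dose and cholinergic-drug use make six. A yes/no code for drug use cannot vary, because all patients take a cholinesterase inhibitor. That leaves five.

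**Step 1: try to reproduce the stated power (no covariates).**

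- Fisher approximation: power = Phi(atanh(0.59) x sqrt(n-3) - 1.96), with atanh(0.59)=0.678. At n=12: 0.678 x 3 - 1.96 = 0.07, power 0.53. At n=18: 0.678 x 3.873 - 1.96 = 0.66, power 0.75.
- t test of the correlation in bivariate normal data (simulated): see the table.
- Fixed-predictor noncentral F, lambda = n x 0.3481/0.6519 = 0.534n: see the table.

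| Unadjusted test | n=12 | n=15 | n=18 |
|---|---|---|---|
| Two-sided, random predictor | 0.56 | 0.68 | 0.77 |
| Two-sided, fixed predictor | 0.63 | 0.74 | 0.83 |
| One-sided, random predictor | 0.69 | 0.79 | 0.86 |

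None reaches .95. At n=12 the smallest significant correlation is 0.576, so a true 0.59 sits almost on the threshold.

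**Step 2: n needed for 0.95.** Fisher: 3 + ((1.960+1.645)/0.678)^2 = 31.3. The simulated t test first passes 0.95 at n=31, and the fixed-predictor formula at n=27.

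**Step 3: one composite binding value plus covariates.** Residual df = n-2-k for k covariates. The correlation with the composite is held at 0.59, and the covariates are assumed independent of binding and to explain no DCFS variance.

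| Covariates | n=12 | n=15 | n=18 |
|---|---|---|---|
| Five, random predictors | 0.30 (df 5) | 0.47 (df 8) | 0.61 (df 11) |
| Six, random predictors | 0.24 (df 4) | 0.42 (df 7) | 0.56 (df 10) |
| Five, fixed predictors | 0.53 | 0.70 | 0.81 |

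**Step 4: three hubs with five covariates.** The inter-hub correlation is assumed to be 0.5 to 0.8, and the composite is assumed to carry all the signal. Separate tests with Bonferroni: 0.21-0.24, 0.35-0.38 and 0.47-0.52. A joint 3-df test: 0.12, 0.24 and 0.37, on residual df n-9 = 3, 6 and 9.

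**Step 5: covariates that do explain DCFS variance.** If the covariates explain a share q, the effect ratio becomes 0.3481/(1-0.3481-q). With five covariates, power is 0.47 at n=12 for q=0.30, 0.60 at n=15 for q=0.20, and 0.74 at n=18 for q=0.20. For q=0.50 the ratio is 0.3481/0.1519 = 2.29, and power is about 0.98 at n=18 but about 0.75 at n=12.

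**The case against.** The strongest reply is that this is a small R21 study, and that the gaps around the power figure are mostly missing detail rather than error. Much of that stands, and several stronger readings that a reader might infer are not supported:

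- *The model has no random effects.* The plan does mention them; it does not say which. One record per patient is inferred from the cross-sectional design and bilateral averaging. Stacking the hubs would make a patient effect estimable, but the plan does not say that this is intended.
- *False positives are uncontrolled.* Two paragraphs promise correction. An error rate of 0.13-0.16 from choosing among hub analyses without correction describes something the plan disclaims. What is missing is the family.
- *The choice is deferred until the data are seen.* No passage says so.
- *No version can reach .95.* This is too absolute: Step 5 gives 0.98 at n=18 if covariates explain half the DCFS variance. The plan makes no such assumption.
- *The covariate list should be cut to age and sex.* This is a trade-off. If motor severity, MoCA and levodopa dose are left out and each correlates 0.5 with binding and with DCFS, the age-and-sex test rejects in 0.19 to 0.47 of studies with no direct association.
- *A composite is required.* It is not better in every case. The joint figures in Step 4 also rest on the assumption least favourable to the joint test.

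Listing DCFS among the predictors and writing Type II for Type I are slips of wording. With a composite, the t statistic is the same whichever variable is the outcome.

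None of this rescues the stated power. It fails for the simplest reading, one unadjusted correlation.

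**Conclusion.** The power claim is wrong as written for this design. For the test it describes, two-sided power is 0.56 to 0.77 over n=12 to 18 (0.63 to 0.83 by the fixed-predictor formula). About 31 patients (or 27) would be needed for 0.95. With the planned covariates and one composite, power is about 0.30 to 0.61 (five) or 0.24 to 0.56 (six). It is lower for three hubs under the Step 4 assumptions.

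The unadjusted figures need only r=0.59, alpha 0.05 and n. The adjusted figures also assume independent covariates that explain no DCFS variance, and they rise if that is untrue. The 0.59 itself was seen in a different disease group and for a different outcome, so its use for DCFS in Lewy body dementia is a further assumption that the plan does not defend.

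The unstated hub handling, correction family, random term, motor scale and drug coding are real but smaller gaps. They matter here because they decide which power figure applies.

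**What to change.** Replace the claim of power above .95 with the power at n=12 to 18 for the model that will be used. State sidedness, the source of the effect size and what is assumed about the covariates.

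In the same paragraph, before analysis:

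1. Name the test that decides Aim 1: one COTC composite, or the three hubs with a named correction family.
2. State the random term and its grouping unit, or use ordinary linear regression for the cross-sectional Aim 1 data. Mixed models can stay for the pre/post data of Aim 2.
3. Name one motor scale. General methods already commits to the MDS-UPDRS: "Severity of motor parkinsonism will be assessed using the Movement Disorder Society-revised".
4. Drop the yes/no cholinergic-drug term or code it so that it varies.
5. Correct the two wording slips.

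Composite versus separate hubs, and whether motor severity, MoCA and levodopa dose stay in the primary model, are the sponsor's decisions. They need only be fixed in advance.

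The cost is some rewritten text and a less favourable stated power. No new patients, visits or data are needed.
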